11.6 New York Heart Association (NYHA) classification

Subject improvement after valve implant will be determined by the McNemar-Bowker (extension of McNemar test to more than two categories) to test, at 90% two-side significance level, the marginal homogeneity between pre-operative and post-operative NYHA proportions. Besides, the NYHA classification will be summarized in a shift table by overall and, for the appropriate visits, by subgroup defined in Section 5.3.

Evaluation performed in corresponding of first and second CT scan visits will be displayed also categorizing by subject with/without reduction leaflet motion and within each leaflet motion category (normal, mildly reduced, moderately reduced, severely reduced and immobile). Number of non-missing observations (n) and percentage on the SAF population will be displayed.

Study: APR002 BELIEVE

A bar plot will be provided to graphically display the overall NYHA marginal percentages, by visit.

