10.1.4. Secondary Endpoint

The secondary endpoints are defined in **Section 6.3.6**. Analysis of the secondary endpoint will be detailed in the Statistical Analysis Plan.

The incidence proportion of reduced leaflet motion up to 1 year post-implant will be evaluated using the same method described for the evaluation of the primary endpoint. The analyses will be done:

- in symptomatic and asymptomatic subjects, based on CT outcomes and anticoagulation or dual antiplatelet therapy modalities, and
- considering relationship to device, procedure, or other causes

Moreover, in subjects in which reduced leaflet motion was previously detected, the proportion of reduced leaflet motion detected through 4D volume-rendered CT-scan with contrast up to 1 year post-implant will be evaluated.

Number of AEs and number of subjects with at least one event will be presented in each group broken down by SAE type. Number of events, as well as number and percentage of subjects, will be tabulated by timing. Linearized rates (90% CIs) will be calculated as number of late (> 30 days) events divided by late subject-years, defined as the subject-years accumulated starting from the $31^{\rm st}$ day after surgery.

Subject improvement after valve implant will be determined by comparison of preoperative and postoperative NYHA functional classifications.

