2.3 SAMPLE SIZE CALCULATION

A sufficient number of subjects will be enrolled in this study to allow a minimum of 75 evaluable CT scans for the primary endpoint. Evaluable scans are those where a determination of normal or abnormal leaflet motion is possible. Considering an attrition rate of 15% of subjects, the sample size targeted for enrollment is approximately 88 subjects.

A sample size of 75 evaluable CT scans produces an Exact two-sided 90% CI with a width lower than 13% when the sample proportion is lower than 10% (evaluation calculated using PASS software, version 13).

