5.1 GENERAL PRINCIPLES

The statistical analysis will be performed on the analysis study database with SAS version 9.4 or above (SAS Institute, Cary, N.C.).

If two or more of the analysis sets as defined in Section 6 coincide or the difference is less than 5%, presentations will only be prepared for the population less restrictive.

The default significant level will be 10%. Confidence Intervals (CIs) will be calculated at 90% confidence level and all tests will be two-sided, unless otherwise specified in the description of the analyses.

All the data collected and derived in the study will be presented in subject data listings.

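### SAP 11.6 determines NYHA improvement with McNemar-Bowker, which tests symmetry rather than the stated marginal homogeneity and cannot show direction

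*SAP*

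**What the plan says.** NYHA class at 1 year is a listed secondary endpoint (Protocol 6.3.6, SAP 11.1). Protocol 10.1.4 asks for a paired comparison and names no test: "Subject improvement after valve implant will be determined by comparison of preoperative and postoperative NYHA functional classifications".

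SAP 11.6 supplies the test: "Subject improvement after valve implant will be determined by the McNemar-Bowker (extension of McNemar test to more than two categories"). The hypothesis it attaches is "the marginal homogeneity between pre-operative and post-operative NYHA proportions", tested "at 90% two-side significance level". The section does not say which post-operative visit enters the test.

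As a further display, "the NYHA classification will be summarized in a shift table by overall" and by subgroup, and a bar plot shows the NYHA percentages by visit.

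On levels, SAP 5.1 reads "The default significant level will be 10" per cent, and adds: "Confidence Intervals (CIs) will be calculated at 90% confidence level and all tests will be two-sided, unless otherwise specified".

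**The concern.** Three things are run together in one sentence: a question (did subjects improve?), a hypothesis (are the two NYHA margins equal?) and a test (Bowker). They do not match.

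- **Test against hypothesis.** Bowker's null is that each off-diagonal cell equals its mirror image. Symmetry implies equal margins, but with more than two classes equal margins do not imply symmetry. The two coincide only in a 2×2 table.
- **Test against question.** Improvement has a direction. Bowker squares each difference and so discards it, and it makes no use of the ordering of the classes.

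Because the SAP says that the test determines improvement, a small p-value could be reported as improvement where the NYHA distribution has not moved, or has moved the wrong way.

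**Working it through.** **Plan's own figure.** No sample size, power or effect size is given for the NYHA test. The only calculated design figure concerns the primary endpoint: "A sample size of 75 evaluable CT scans produces an Exact two-sided 90% CI with a width lower than 13" per cent when the sample proportion is below 10%. It reproduces: at 7/75 (9.3%) the exact 90% limits are 4.46% and 16.82%, a width of about 12.35 points. Nothing below affects it.

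**Inputs.** The test, hypothesis and level come from SAP 11.6 and 5.1. The documents give no NYHA data, so both tables below are assumed. N = 75 is borrowed from the evaluable-scan target. Rows are the pre-operative class, columns the post-operative class.

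**Formulas.**
- Bowker: B = Σ over i<j of (n_ij − n_ji)² / (n_ij + n_ji). It has 6 df for a full 4×4 table, or one per non-empty pair.
- Stuart-Maxwell: d′V⁻¹d, where d is the vector of row total minus column total (one class dropped) and V is its estimated covariance.

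**Table A: identical margins, movement in a cycle**

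| Pre \ Post | I | II | III | IV | Total |
|---|---|---|---|---|---|
| I | 10 | 8 | 1 | 0 | 19 |
| II | 1 | 12 | 8 | 0 | 21 |
| III | 8 | 1 | 24 | 0 | 33 |
| IV | 0 | 0 | 0 | 2 | 2 |
| Total | 19 | 21 | 33 | 2 | 75 |

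- Improved 1 + 8 + 1 = 10; worsened 8 + 1 + 8 = 17; unchanged 48.
- Bowker: three non-empty pairs, each 8 against 1. B = 3 × 7²/9 = 16.33. p = 0.001 on 3 df and 0.012 on 6 df, so it rejects at 0.10 either way.
- Stuart-Maxwell: every element of d is 0, so the statistic is 0 and p = 1.
- In 4,000 multinomial samples of 75 drawn from Table A's proportions, where marginal homogeneity is true, Bowker rejects at 0.10 in 99% and Stuart-Maxwell in 9.7%.

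**Table B: strong improvement**

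| Pre \ Post | I | II | III | IV | Total |
|---|---|---|---|---|---|
| I | 5 | 1 | 0 | 0 | 6 |
| II | 14 | 10 | 2 | 0 | 26 |
| III | 12 | 18 | 8 | 0 | 38 |
| IV | 2 | 2 | 1 | 0 | 5 |
| Total | 33 | 31 | 11 | 0 | 75 |

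- Improved 49, worsened 3, unchanged 23.
- Bowker: 169/15 + 144/12 + 4/2 + 256/20 + 4/2 + 1/1 = 11.27 + 12 + 2 + 12.8 + 2 + 1 = 41.07 on 6 df, p = 2.8 × 10⁻⁷.
- Transposed (3 improved, 49 worsened): again 41.07, with the same p-value.
- Stuart-Maxwell: 37.74 on 3 df, p = 3.2 × 10⁻⁸, also unchanged on transposing. It matches the stated hypothesis but does not give direction either.

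**Sign test on the same tables**, z = (improved − worsened)/√(improved + worsened), against ±1.645 at two-sided 10%:
- A: (10 − 17)/√27 = −1.35, not rejected.
- B: (49 − 3)/√52 = +6.38, rejected towards improvement.
- B transposed: −6.38, rejected towards worsening.

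**Level.** Taken literally, a 90% significance level has a 6-df critical value of 2.20, against 10.64 at 10%. SAP 5.1 settles which is meant.

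**The case against.** The strongest reply is that this will rarely matter in practice. Table A is contrived: subjects circulate among classes I to III so that the margins cancel exactly. Real data after valve replacement should move mostly one way, and Protocol 2.3.1 reports improvement in NYHA class for most subjects in an earlier study of this valve. With movement like that in Table B, Bowker and Stuart-Maxwell both reject overwhelmingly. The shift table and bar plot would also expose a rejection with unmoved or worsened classes. Protocol section 10 calls the study descriptive and non-confirmatory, and no success criterion rests on this p-value.

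All of that stands, and it limits the weight of the point. It does not remove it. The displays are planned in addition to the test, and it is the test that the SAP says determines improvement. Even where Bowker rejects because subjects improved, the p-value does not establish that they did.

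A reader might go further and infer that the trial will report a false improvement. The documents do not support that: they hold no NYHA data, and a counterexample shows only that the test and the hypothesis differ. A reader might also infer from the 90% wording that the test would be run at alpha = 0.90. The 10% default in SAP 5.1, with its 90% confidence intervals, makes this a slip between confidence and significance.

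**Conclusion.** The mismatch is real and of modest consequence. With four classes, the named test addresses symmetry, not the marginal homogeneity stated for it, and it cannot distinguish improvement from deterioration. Both facts are mathematical and need no assumption about the trial's data. The sizes in Table A (p = 0.001 against p = 1) depend on an extreme assumed pattern and mark what is possible, not what is likely.

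The consequence is confined to one secondary endpoint in a descriptive, single-arm study whose planned displays already show direction. The primary endpoint and the sample size are untouched. The 90% level is an editorial correction.

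**What to change.** In SAP 11.6:

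1. Replace McNemar-Bowker with a paired ordinal test of class change from pre-operative to 1 year (Wilcoxon signed-rank or sign test), two-sided at alpha 0.10. Naming the 1-year visit matches the endpoint and closes the gap over which post-operative assessment is used.
2. Report the proportions improved, unchanged and worsened with 90% CIs, among subjects with both assessments. Keep the shift table and bar plot.
3. If a test of marginal homogeneity is also wanted, use Stuart-Maxwell or Bhapkar and note that it does not show direction. On its own it would repair the hypothesis but leave the improvement question unanswered.
4. Change the stated level to a 10% two-sided significance level, consistent with SAP 5.1.

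The cost is about one rewritten SAP sentence, a change-history entry and a different SAS procedure call. No new data are needed. Protocol 10.1.4 names no test, so its wording can stay as it is.

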12 SECONDARY PERFORMANCE ANALYSIS

12.1 SECONDARY PERFORMANCE ENDPOINT

The secondary performance endpoint for the study will be evaluated in the SAF and is:

 Hemodynamic performance up to 1 year post-implant through TTE assessed by Echocardiographic Core Lab.

12.2 HEMODYNAMIC PERFORMANCE

Hemodynamic performance of Perceval prosthetic heart valve will be assessed by flow velocities, pressure gradients, effective orifice area and degree of regurgitation. Descriptive statistics will be displayed by visit (overall and, for the appropriate visits, by subgroup defined in Section 5.3) as reported in the following sections. Evaluation performed in corresponding of first and second CT scan visits will be displayed also categorizing by subject with/without reduction leaflet motion and within each leaflet motion category (normal, mildly reduced, moderately reduced, severely reduced and immobile).

12.2.1 Flow velocities, Pressure gradients and effective orifice area

Hemodynamic performance will be presented as per Core Lab results. Actual values will be analyzed appropriately at each assessment visit.

The following parameters will be analyzed appropriately:

- Left ventricular internal dimension-diastole (LVIDd) [cm]
- Left ventricular internal dimension-systole (LVIDs) [cm]
- Interventricular septal thicknesses-diastole (IVSd) [cm]
- Left ventricular posterior wall diameter (PWd) [cm]
- Left ventricular mass [g]
- Left atrium diameter [cm]
- Left atrium volume [mL]
- Left ventricular end-diastolic volume (LVEDV) [mL]
- Left ventricular end-systolic volume (LVESV) [mL]
- Ejection fraction (EF) [%]
- Mitral E [cm/sec] (early diastolic velocity from mitral inflow Doppler)
- Mitral A [cm/sec] (late diastolic velocity from mitral inflow Doppler)

COPYRIGHT LIVANOVA. ALL RIGHTS RESERVED. MAY NOT BE REPRODUCED WITHOUT PERMISSION. ALL HARD COPIES SHOULD BE CHECKED AGAINST THE CURRENT ELECTRONIC VERSION WITHIN MASTERCONTROL PRIOR TO USE AND DESTROYED PROMPTLY THEREAFTER. ALL HARD COPIES ARE CONSIDERED UNCONTROLLED DOCUMENTS.

- Mitral valve deceleration time [L/min]
- Septal E [cm/sec] (early diastolic velocity recorded from tissue Doppler at the septal mitral annulus)

Study: APR002 BELIEVE

- Septal A [cm/sec] (late diastolic velocity recorded from tissue Doppler at the septal mitral annulus)
- Tricuspid regurgitation velocity [m/sec]
- Right atrium pressure IVC diameter [mmHg]
- Right ventricular systolic pressure (RVSP) [mmHg]
- Left ventricular outflow tract (LVOT) diameter [cm]
- LVOT CSA [cm²]
- LVOT velocity [m/sec]
- LVOT TVI [cm]
- LVOT peak gradient [mmHg]
- LVOT mean gradient [mmHg]
- Aortic peak velocity [m/sec]
- Aortic TVI [cm]
- Aortic peak gradient [mmHg]
- Aortic mean gradient [mmHg]
- Effective orifice area (EOA) TVI [cm2]
- EOA velocity [cm2] (orifice area by velocity method)
- Heart rate [bpm]
- Stroke volume [mL]
- Cardiac output [L/min]
- Stent perimeter [mm]
- Stent major axis [mm]
- Stent minor axis [mm]
- Stent area [mm²]

Median and quartiles will be displayed graphically by visit for the following parameters: EF [%], aortic peak gradient [mmHg], aortic mean gradient [mmHg], EOA TVI [cm2].

Additional specific analyses may be performed to evaluate the geometrical data. Details of any such analyses will be documented in an ancillary SAP.

12.2.2 Degree of regurgitation

Presence of aortic regurgitation (and specifications of location and degree) will be summarized appropriately. Shift tables will be also displayed to evaluate the severity changes over time.

The following Core Lab variable will be displayed:

Aortic regurgitation

COPYRIGHT LIVANOVA. ALL RIGHTS RESERVED. MAY NOT BE REPRODUCED WITHOUT PERMISSION. ALL HARD COPIES SHOULD BE CHECKED AGAINST THE CURRENT ELECTRONIC VERSION WITHIN MASTERCONTROL PRIOR TO USE AND DESTROYED PROMPTLY THEREAFTER. ALL HARD COPIES ARE CONSIDERED UNCONTROLLED DOCUMENTS.

LN-GLB-CLN-TEM-0033 rev1 Page 24 of 42

- Total aortic regurgitation severity
- Paravalvular severity
- Transvalvular severity

12.2.3 Valve re-intervention

Overview tables on valve re-intervention will be generated by overall using the SAF:

- 1) Summary of the number and percentage of subjects with at least one:
- valve re-intervention
- valve re-intervention with valve explants
- re-intervention without valve explants
- valve in valve procedure

The percentage denominator will be the number of subjects in the SAF.

2) For subject with at least one re-intervention with valve explants or valve in valve procedure, summary of the number and percentage of subjects:

Study: APR002 BELIEVE

- with at least one another valve implanted
- survived
- died

The percentage denominator will be the number of subjects with at least one re-intervention with valve explants or valve in valve procedure.

- 3) If >5% of subjects with more than one re-intervention, summary of the number and percentage of re-intervention for:
- valve re-intervention
- valve re-intervention with valve explants
- re-intervention without valve explants
- valve in valve procedure

The percentage denominator will be the total number re-interventions.

4) If >5% of subjects with more than one re-intervention with valve explants or valve in valve procedure, summary of the number and percentage of re-intervention with at least one another valve implanted. The percentage denominator will be the number of re-interventions with valve explants or valve in valve procedure.

All re-intervention details will be listed in subject listing sorted by and subject ID.

13 SECONDARY SAFETY ANALYSIS

All safety data will be presented for the SAF and will be summarized descriptively by overall and, where specified, by occurrence of enrollment (subjects enrolled at implant/after implant) and/or study period (post-implant and post-ACT/DAPT).

Study: APR002 BELIEVE

13.1 ANALYSIS OF SERIOUS ADVERSE EVENTS

Only SAEs are to be recorded in this study.

The causal relationship of SAEs to procedure or device is categorized as follows:

Category	Assessment by investigator/sponsor/CEC:
Related	Definitely related
	Probably related
Not related	Not related
Unknown	Unknown

To be in line with the CIP, "Probably related" assessment will be reworded in order to read "Likely related" in the Statistical Outputs.

A device related SAE is considered to be expected if specifically marked as "Expected" in the "Expectedness" field of e-CRF; otherwise it will be considered "Unexpected".

Where a SAE relationship will be further judged by Sponsor or CEC, only the final assessment will be analyzed by means of the following judgment order: 1. Site, 2. Sponsor, 3. CEC.

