12. SAFETY REPORTING

The Sponsor is responsible for the ongoing safety evaluation of the study device, review of reported SAEs, investigation of UADEs, and notification of regulatory authorities per applicable requirements (For this study, only SAEs will be reported.). The Sponsor is also responsible for training the investigational staff prior to start the study on any study-related procedures, including reporting of SAEs. The Sponsor, through the Clinical Safety Office, will provide oversight of general SAE handling procedures for the clinical study and can assist the PIs and various committees in conducting a medical review of reported SAEs.

The PI is responsible for ensuring the safety and well-being of the subjects enrolled in their clinical site and should report events to the Sponsor, IRB, and regulatory bodies as described in this Section.

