12.1. PRINCIPAL INVESTIGATOR'S RESPONSIBILITIES IN SAE REPORTING

The PI is required to report all SAEs to the Sponsor including mortality, valve reintervention, myocardial infarction, structural valve deterioration, moderate or severe valve regurgitation, valve endocarditis, valve thrombosis, thromboembolic events, hemolysis, major bleeding and other clinical endpoints.

Table 5 SAE Reporting to the Sponsor

	Subject Visit				
	Discharge	Early Post-op (1-6 Mo.)	Late Post-op (6-9 Mo.)	1 Year (11-13 Mo.)	
All Deaths, UADEs, and SAEs	X	х	Х	Х	

The following timelines for reporting should be followed (**Table 6**):

- UADEs should be reported to the Sponsor immediately within 24 hours of awareness of the event(s) by notifying the Clinical Project Manager (or designee) and by entering the information in the EDC. These events require urgent investigation by the Sponsor and reporting to regulatory authorities, as applicable.
- SAEs should be reported as soon as possible but no later than 10 calendar days
 of awareness. The PI should enter all available information in the SAE section of
 the EDC system.

Table 6 Timelines and Communication Methods for Reporting SAEs

Event Classification	Communication Method	Communication Timeline
SAEs including deaths and Adverse Device Effects	Complete the AE eCRF page with all available information.	Within 10 calendar days of first becoming aware of the event or as per local/regional regulations.
	Provide all relevant source documentation (unidentified) for the reported event.	Reporting of any updated information required through the end of the study When documentation is available.
UADE	Contact the Clinical Project Manager (or designee).	Within 24 hours of awareness.
	Complete the SAE eCRF page with all available information.	

- a) The PI should perform the following assessments for each reported SAE:
 - Identify the clinical event term or description
 - Seriousness/severity of the event
 - Relationship of the event to the device, procedure, and/or medications
- b) The PI should provide all the information needed to complete the AE eCRF.
- c) The PI is responsible for informing the IRB of SAEs as required by local/regional regulations and IRB.
- d) The PI is expected to assist in clinical review and supply the Sponsor with relevant source documents and results of ancillary procedures required in the protocol.

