13.3. CLINICAL EVENTS COMMITTEE

A Clinical Events Committee (CEC) will be established for this study. The members of the CEC will be independent of the Sponsor and the PIs. The committee will be composed of physicians with expertise in the following fields, but not limited to: cardiothoracic surgery, cardiology (echocardiography), and neurology. The details of operations and activities are described in the CEC Charter.

The CEC activities will be coordinated by the Sponsor. This committee will adjudicate the following related to the clinical events cited in the primary and secondary endpoints:

- Endpoints or event type according to clinical study protocol definitions: valve reintervention, myocardial infarction, all-cause mortality, structural valve
 deterioration, moderate or severe valve regurgitation, valve endocarditis, valve
 thrombosis, thromboembolic events, hemolysis, major bleeding and other clinical
 endpoints according to clinical study protocol definitions.
- Relationship of the event to the device and/or procedure
 - Not related: The SAE is clearly not or doubtfully related to the device/procedure.
 - Likely related: The SAE may be related to the device/procedure.
 - Definitely related: There is a clear and documented relationship or causality between the SAE and the device or the procedure.
 - Unknown if related: The relationship between the SAE and the device/procedure cannot be assessed or there is insufficient information available to perform this assessment.
- Review and provide clinical input to a site-reported Unexpected (Serious) Adverse
 Device Effect (UADE).
- Other SAEs as requested by the Sponsor.

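### Where the sponsor re-judges an SAE that the CEC does not adjudicate, the sponsor's relatedness category replaces the site's in the tables, a step the protocol does not describe

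*SAP*

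**What the plan says.** **SAP 13.1** heads its relatedness categories "Assessment by investigator/sponsor/CEC", so all three parties may supply the analysed value. The categories are definitely related, probably related (printed as likely related to match the protocol), not related and unknown. The selection rule is "Where a SAE relationship will be further judged by Sponsor or CEC, only the final assessment will be analyzed", with the "judgment order: 1. Site, 2. Sponsor, 3. CEC".

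**Protocol 12.1** has the investigator assess, for each reported SAE, the "Relationship of the event to the device, procedure, and/or medications".

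**Protocol 13.3** sets up the committee: "The members of the CEC will be independent of the Sponsor and the PIs". Its remit is: "This committee will adjudicate the following related to the clinical events cited in the primary and secondary endpoints". The items below that sentence include event type and relationship to device or procedure. The committee also gives clinical input on unanticipated device effects reported by sites. Everything else falls under "Other SAEs as requested by the Sponsor".

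**Protocol 12** makes the sponsor responsible for ongoing safety evaluation and for reviewing reported SAEs. It adds that the sponsor's safety office "can assist the PIs and various committees in conducting a medical review of reported SAEs".

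**SAP 3.1** declares no change in analysis from the protocol. It mentions only the added per-protocol set.

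**The concern.** Read together, these sections leave a group of SAEs for which the sponsor controls both the second judgement and whether an independent third one follows. For those events the sponsor's category is the one tabulated. Nothing limits the direction of a change, and nothing in either document requires a site-sponsor disagreement to go to the CEC.

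The study is single-arm and concerns the sponsor's own valve. It has no DSMB (Protocol 13.2), and the sponsor's own biometrics department runs the analysis (SAP 1). The CEC is therefore the main independent check on relatedness, and this route can bypass it. What is at stake is the credibility of the related-SAE tables, where counts may be small enough for one or two reclassifications to be visible.

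**Working it through.** The plan states no figure on this point, so the check is mainly textual.

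**Step 1: which assessment is analysed.** The order could be read as a priority list with the site first. But the rule speaks of further judgement and of a final assessment, and under a site-first reading the sponsor and CEC steps would have no function. The sequential reading is the natural one: a later judgement replaces an earlier one.

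**Step 2: which events reach the CEC.** Protocol 13.3 names all-cause mortality, valve re-intervention, myocardial infarction, structural deterioration, moderate or severe regurgitation, endocarditis, valve thrombosis, thromboembolism, hemolysis, major bleeding, and other clinical endpoints as the protocol defines them. Pacemaker implantation is analysed as an outcome in SAP 11.5, but it is neither on that list nor among the endpoints in Protocol 6.3.6. It is a concrete example of an event that may fall outside the default remit.

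**Step 3: apply the rule case by case.** The last column uses the rule proposed under the fix.

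| Site | Sponsor | CEC | Analysed under SAP 13.1 | Analysed under the fix |
|---|---|---|---|---|
| any | any | adjudicates | CEC | CEC |
| likely related | no further judgement | none | likely related | likely related |
| likely related | not related | none | not related | likely related |
| not related | likely related | none | likely related | likely related |
| likely related | unknown | none | unknown | likely related |
| unknown | not related | none | not related | unknown |

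The two rules differ only where the sponsor makes a less related call than the site and the CEC does not adjudicate.

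**Step 4: which outputs change.**
- SAP 13.1.1 and 13.1.2: the rows by procedure relatedness and by device relatedness, and the device-related subset within the expectedness rows. Expectedness itself comes from its own e-CRF field.
- Linearized rates in SAP 13.1.2: the relatedness rows only. The overall rates do not use relatedness.
- The listing of unexpected device-related SAEs: an event moved to not related drops out of it.
- Unchanged: total SAE counts, SAEs leading to termination or death taken overall, the primary endpoint (a Core Lab reading, SAP 10.3), and freedom from valve safety events (analysed by event type, SAP 11.5).

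**Step 5: scale.** Input: about 88 enrolled subjects (SAP 2.3). Assumptions: all 88 are in the safety population, and the reclassified SAE is that subject's only one in the related category.

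- One subject: 1/88 = 0.0114, or 1.1 percentage points.
- Two subjects: 2/88 = 0.0227, or 2.3 percentage points.

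Neither document gives an expected number of SAEs outside the CEC's remit or a rate of sponsor re-judgement, so the total effect cannot be computed.

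**The case against.** A good deal can be said for the plan as written.

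- **The rule is conditional.** It applies only where the sponsor makes a further judgement. A reader might infer that the sponsor overrides the investigator on every non-endpoint SAE, but neither document says so. Without a further judgement the site's category stands. This stands.
- **The rule is symmetric.** A reader might infer that counts will be pushed down. The sponsor can equally raise them, and no text or figure shows a direction. This stands: the issue is one party's control, not demonstrated bias.
- **The site's view is not hidden.** SAP 5.1 commits to listing all collected and derived data, and the site's assessment is collected data. The accurate statement is that no table by assessor is planned. Listings help transparency but do not alter the tabulated counts.
- **CEC coverage is wide.** The serious valve-related events go to the committee, and site-reported unanticipated device effects reach it without a sponsor request, though giving clinical input may be less than formal adjudication. The CEC charter is not available here and might require referral of disagreements. This narrows the affected group to mainly non-endpoint SAEs.
- **The protocol does not forbid the step.** It gives the sponsor an SAE review role and leaves analysis detail to the SAP, and SAP 3.2 records the rule as added in version 2.00. A reader might infer a contradiction between the documents. There is none, only silence. But the protocol places relatedness with the investigator and the CEC, and Protocol 10.4 asks for relevant analysis changes to be stated with a rationale.
- **No endpoint depends on it.** The study is descriptive, and SAE relatedness enters neither the primary endpoint nor the listed secondary endpoints. This stands and limits the consequence to safety reporting.

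**Conclusion.** The point holds in conditional form. Where the sponsor further judges an SAE that the CEC does not adjudicate, the sponsor's category displaces the site's in the outputs identified above. The device maker alone can then lower or raise related-SAE counts through a step that the protocol does not describe and SAP 3.1 does not declare.

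The size is 1.1 percentage points per reclassified subject on the assumptions stated, and in a rare category that could separate zero from non-zero. The overall effect is unknown and may be nil if the sponsor never departs from the site. The conclusion rests on the sequential reading of the order and on no unseen charter provision sending disagreements to the CEC. It is a worthwhile and inexpensive improvement to safety reporting, not a threat to the study's main result.

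**What to change.** 1. **SAP 13.1:** analyse the CEC assessment where there is one. Otherwise analyse the more related of the site and sponsor assessments, ranked definitely related, likely related, unknown, not related. The ranking has to place unknown explicitly, because the SAP treats it as its own category.
2. **SAE listing:** show the site, sponsor and CEC assessments side by side for each event.
3. **SAP 3.1:** declare the sponsor assessment step as an addition to the protocol, with its rationale.

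An alternative for item 1 is to refer every site-sponsor disagreement to the CEC, which costs committee time. The proposed rule needs one derivation line, one listing layout and one sentence, and no new data from subjects or sites. Its downside is that related counts may be slightly higher, since a sponsor downgrade no longer takes effect without the CEC. If the sponsor never makes a less related call than the site, the tables do not change and the listing shows it.
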